5.4. Subject Withdrawal from the Study

A subject may be withdrawn from the study at any time at the discretion of the Investigator.

Justifiable reasons to discontinue a subject from the study may include, but are not limited to, safety, ability or willingness to comply with conditions of the protocol, withdrawal of consent, lost to follow-up, Investigator discretion, Sponsor decision, or premature termination of the study.

The reason(s) for premature discontinuation will be documented on the subject's CRF.

Any AEs or SAEs that lead to study discontinuation should be followed as appropriate until the AE has resolved or stabilized (in the opinion of the Investigator and Sponsor Medical Monitor).

Subjects who prematurely discontinue after receiving a dose of study drug, should continue to be followed for scheduled safety assessments according to the SOE ([Table 2](#)), if possible. At a minimum, every attempt should be made to complete the Week 4 / Premature Discontinuation procedures; however, subjects are free to withdraw consent from participation in the study at any time, without prejudice to their medical care.

If a subject is lost to follow-up (i.e., fails to return for study visits), all reasonable efforts should be made to contact the subject and complete the Week 4 / Premature Discontinuation procedures.

Should it be discovered after a subject has begun study treatment that the subject did not meet all inclusion and exclusion criteria, or if during the study a subject ceases to meet all inclusion and exclusion criteria, the subject's continued participation in the study will be discussed with the Medical Monitor.

5.5. Premature Termination of the Study

If the study is prematurely terminated, written notification, documenting the reason for study termination, will be promptly provided by the Sponsor to the regulatory authorities. The Investigator will be responsible for informing the IRB.

The Sponsor reserves the right to terminate the study for any reason at any time.

6. STUDY TREATMENTS, MATERIALS, AND MANAGEMENT

6.1. Description of Study Drug

The study drug code name is SP-624. SP-624 is [REDACTED]
[REDACTED] intended for the treatment of MDD.

The clinical trial material for this study will consist of capsules, each containing 10 mg of SP-624 API. Matching placebo capsules identical in shape and color to the active capsules will also be used.

6.2. Acquisition of Study Drug Supplies

After the research site has submitted all approved regulatory and study start-up documents, the Sponsor will initiate a requisition for an initial shipment of study kits to be delivered to the site via the Sponsor's distribution facility.

All manufacturing, packaging, and labeling operations for the supplied study drug materials will be performed according to Good Manufacturing Practice (GMP) and GCP guidelines, as well as local regulations.

Storage and retest information will be provided for all supplied materials.

Upon receipt of the materials, the Investigator or designee will examine the package container, labeling, and appearance of the packaged materials to confirm the packaged materials were received in good condition.

All study materials will be stored at the study site in a restricted-access, securely locked area, under controlled temperature and humidity conditions in accordance with the manufacturer's instructions (see Section [6.7](#)).

6.3. Subject Treatment Assignment

When the decision is made to randomize a subject, the Investigator should pick the next randomization number from the study drug kits assigned to the site. The subject randomization number will be recorded in the CRF.

6.4. Study Drug Administration

Each dose of SP-624 will be supplied as two capsules, each containing 10 mg of API. Matching placebo capsules identical in shape and color to the active capsules will also be used. Following successful completion of the Baseline Visit, subjects will be randomized in a 1:1 ratio to one of two treatment groups:

- Treatment Group #1: Two 10 mg capsules SP-624 each morning for 4 weeks
- Treatment Group #2: Two capsules placebo each morning for 4 weeks

Each study drug dose should be taken orally, once daily at approximately the same time each morning. Study drug doses should be taken on an empty stomach before breakfast, and no food should be consumed for at least 1 hour after dosing. High fat foods at breakfast (e.g., bacon,

cheese, eggs, etc.) should be avoided. Morning liquids such as coffee or tea are allowed without any additives (eg, cream, sugar, etc).

If dosing on an empty stomach is not practical or not well tolerated, then a low fat, low calorie breakfast 2 hours before dosing, or 30-60 minutes after dosing, is acceptable. If dosing remains not well tolerated, then subjects should dose 30 minutes after a low fat, low calorie meal.

Study drug will be packaged in subject kits and each kit will contain four weekly blister cards with each card containing 20 capsules of study drug (two capsules per dose for seven days of dosing, plus three extra days of dosing as a provision for study visit scheduling). Each subject kit will be labeled with a 3-part label that specifies the randomization number, cautionary statement, and storage conditions. Each blister card will have a one-part label that specifies the randomization number, week, number of capsules, cautionary statement, and storage conditions.

Study drug will be dispensed as follows:

- Baseline Visit – one blister card for Week 1
- Week 1 Visit – one blister card for Week 2
- Week 2 Visit – one blister card for Week 3
- Week 3 Visit – one blister card for Week 4

Subjects will be instructed to return study drug at the Week 1, Week 2, Week 3, and Week 4 (or Premature Discontinuation) Visits.

If the two capsule dose, is not well tolerated, the dose can be decreased to one capsule per dose after Week 1.

6.5. Treatment Compliance

Study drug accountability will be recorded by study site staff, and any deviations from the administration instructions or dosing schedule will be entered into the subject's CRF.

6.6. Study Drug Accountability

The Investigator (or designee) is responsible for the accountability, reconciliation, and record maintenance of all study drug receipt, use, and disposition. In accordance with all applicable regulatory requirements, the Investigator or designated study personnel must maintain study drug accountability and storage records throughout the study. Unused drug will be returned to the investigative site and to the Sponsor or designee at the end of the study for destruction. No study drug usage outside the protocol will be allowed.

When a kit is assigned to a subject, the Investigator will tear off a 2 part segment of the label that contains a tamper-evident covered disclosure panel to be used for unblinding in case of emergency and affix the 2-part segment to the drug dispensing record. The drug dispensing record will be collected for the sponsor's files at the end of the study. This will serve to connect the unique randomization number to the unique subject identification number assigned at Screening.

6.7. Study Drug Storage and Stability

All study materials will be stored at the study site in a restricted-access, securely locked area, under controlled temperature and humidity conditions in accordance with the manufacturer's instructions.

The storage conditions for the study drug will be indicated on the label.

All supplied study drug materials will be stored at the study site in a restricted-access, securely locked area at the long-term refrigerated storage condition, 2-8°C. After a study drug kit has been assigned to a subject, the study drug kit and weekly blister cards dispensed to study subjects may be stored under room temperature conditions, 25°C (77°F), with excursions permitted between 15°C and 30°C (59°F-86°F).

In the solid state, the SP-624 drug substance is stable for at least 18 months when stored at 5°C and for at least 6 months when stored at 25°C/60% relative humidity.

SP-624 drug product stability is expected to directly correlate with that of the drug substance, since the drug product is neat drug substance filled into capsules. A 24-month stability program will be initiated for these capsules once manufacturing is completed, with storage conditions at 2-8°C and 25°C/60% relative humidity. Retest date information for the study drug will be provided.

At the Week 1, Week 2, Week 3, and Week 4 Visits, subjects will return the previously used blister cards, including any unused study drug. The used study drug kits will be maintained at the site under room temperature storage conditions until returned to the Sponsor or designee.

6.8. Prior and Concomitant Medications

Medications taken within 28 days before Day 1 will be documented as prior medications. Medications taken any time on or after Day 1 and until completion of the Week 4 / Premature Discontinuation Visit will be documented as concomitant medications. Medications that started after the date of the last dose of study drug will not be considered concomitant but will be considered post-treatment.

The use of all prior, concomitant, and post-treatment medications will be recorded in the subject's CRF, including the drug name, dose, route of administration, dates of administration, and indication.

Once all Screening assessments have been completed, any current psychoactive medications and supplements must be discontinued. Subjects should consult with the Investigator before taking any medications, including over-the-counter products.

Subjects may be treated with anti-depressant medications according to physician recommendations after completion of the Week 5 Visit unless a clinically significant lab value is identified at the Week 4 Visit. If a clinically significant lab value is identified at the Week 4 Visit, consult with the Medical Monitor to determine if the lab value needs to be followed prior to initiating new therapy.

Previous medications for medical, non-psychiatric illnesses, as well as oral contraceptives and contraceptive devices, are permitted.

Medications such as non-steroidal anti-inflammatories, antacids, and non-psychoactive allergy medications, may be given at the discretion of the Investigator.

A list of restricted and prohibited medications is included in [Table 4](#):

Table 4: Restricted and Prohibited Medications

Medication Class	Examples ¹	Comment
Antidepressants	Trazodone TCAs SSRIs SNRIs MAOIs	All prohibited Any anti-depressants being taken at the time of Screen must be discontinued within a time period prior to Baseline corresponding to at least five half-lives of the medication in question.
Antipsychotics	Aripiprazole Brexpiprazole Haloperidol Olanzapine Risperidone	All prohibited If an antipsychotic was used to treat the current episode of depression, the subject should be excluded.
Anxiolytics	Benzodiazepines	Restricted Subjects on a stable dose of lorazepam (2 mg/day), or equivalent dose of another benzodiazepine (e.g., diazepam 15 mg), for anxiety at the time of Screening may continue with the current treatment regimen. The dose should remain consistent throughout the study. Should a benzodiazepine be required for increased anxiety during the study in a subject who had not been taking a consistent dose prior to Screening, lorazepam 2 mg/day, or an equivalent dose of another benzodiazepine (e.g., diazepam 15 mg), is limited to two days or less per week. Use the night before or the day of a study visit (prior to the visit) is prohibited. Any need to exceed this amount must be discussed with the Medical Monitor.
Hypnotics	Zolpidem Temazepam Sedating antihistamines	Restricted Zolpidem being taken daily for sleep at the time of the Screening visit is permitted for severe insomnia. The dose should remain consistent throughout the study. If zolpidem is being taken as needed at the time of Screening, use is limited to three nights or less per week and use the night before a study visit is prohibited. Prohibited All other hypnotics

Medication Class	Examples ¹	Comment
Mood stabilizers and anticonvulsants	Lithium Valproate Lamotrigine Gabapentin	All prohibited Any mood stabilizers or anticonvulsants being taken at the time of Screening must be discontinued within a time period prior to Baseline corresponding to at least five half-lives of the medication in question.
Muscle relaxers	Carisoprodol Cyclobenzaprine Metaxalone Baclofen	Restricted Use of muscle relaxants during the study is limited to episodic use for an acute situation (e.g., back injury during the study) and must be discussed with the Medical Monitor.
Opioid analgesics	Oxycodone Morphine Tramadol Codeine	Restricted Use of opioids during the study is limited to episodic use for an acute situation (e.g., back injury during the study) and must be discussed with the Medical Monitor.
Stimulants	Amphetamine Dextroamphetamine Pemoline Methylphenidate	All prohibited Any stimulants being taken at the time of Screening must be discontinued within a time period prior to Baseline corresponding to at least five half-lives of the medication in question.
Herbal and nutritional supplements	St. John's Wort Ginkgo Biloba S-Adenosyl methionine (SAM-e) Omega-3 supplements Cannabidiol products Melatonin	Restricted Only multivitamins that do not contain any of the example ingredients are allowed during the study.

¹ Medications including, but not limited to, examples provided.

7. STUDY PROCEDURES AND ASSESSMENTS

7.1. Schedule of Events

The SOE for participants in the study is provided in [Table 2](#).

The actual dates of study drug administration and all study visits and assessments will be recorded in the subject's CRF. If a study visit or assessment occurs outside the specified time point and allowed time window (if applicable), then the reason for the deviation will be noted. Every attempt should be made to ensure that subsequent visits and assessments are performed on-time.

The Screening Period may be extended for extenuating circumstances, such as when additional time is needed for medication taper/washout or to repeat laboratory testing, with the approval of the medical monitor.

Study visits during the Treatment Period can be scheduled within a ± 3 day window relative to the Baseline Visit (i.e., the Week 1 Visit can be scheduled 7 ± 3 days relative to the completion of the Baseline Visit, the Week 2 Visit can be scheduled 14 ± 3 days relative to the completion of the Baseline Visit, the Week 3 Visit can be scheduled 21 ± 3 days relative to the completion of the Baseline Visit, etc.).

The Week 5 Visit can be scheduled 7 ± 3 days relative to the Week 4 / Premature Discontinuation Visit and the Week 6 Visit can be scheduled 14 ± 3 days relative to the Week 4 / Premature Discontinuation Visit.

Whenever ECGs, vital signs, and a blood draw for PK and/or safety labs are scheduled on a given day, the ECG and vital signs should be completed in the sequence of procedures either prior to the blood draw (preferred) or after the blood draw, such that the blood draw does not interfere with the ECG and vital sign recordings.

In addition to the study visits and assessments described in the SOE, unscheduled visits/assessments may be performed or repeated at the discretion of the Investigator if required to further evaluate laboratory parameters or the subject's clinical safety.

7.2. Study-Specific Procedures

7.2.1. Informed Consent

The Investigator must inform each prospective subject of the nature of the study, explain the potential risks, and obtain written informed consent from the subject prior to performing any study-related Screening procedures. Once written informed consent is obtained, prospective subjects will be screened for eligibility into the study based on the inclusion and exclusion criteria detailed in [Section 5](#).

7.2.2. Demographic Information, Medical History/Current Medical Conditions, and Treatment History

Demographic information (e.g., date of birth, sex, race, ethnicity) will be collected and a detailed medical history, including review of past and ongoing medical conditions or procedures will be

obtained during the Screening Period as specified in the SOE ([Table 2](#)). Additionally, treatment history for the current depressive episode will also be collected.

7.2.3. Mini International Neuropsychiatric Interview

Subjects must meet DSM-5 criteria for moderate to severe MDD, as confirmed by the MINI ([Sheehan et. al, 1998](#)). Subjects with a diagnosis of co-morbid GAD may be included if MDD is the primary diagnosis. The MINI should only be completed by Sponsor approved raters. Raters will be approved by the Sponsor based on education and experience conducting the MINI in subjects with MDD.

Current DSM-5 diagnoses of depression with peripartum onset, panic disorder, obsessive compulsive disorder, post-traumatic stress disorder, anorexia nervosa, or bulimia nervosa are exclusionary.

A history of or current DSM-5 diagnosis of MDD with psychotic features, any schizophrenia spectrum and other psychotic disorders, bipolar disorder, or personality disorder are exclusionary.

7.2.4. Assessment of Efficacy

Efficacy assessments will be conducted by individuals with sufficient experience conducting the below rating scales who have received centralized rater training and have been approved by the PI and Sponsor. Whenever possible, the same rater should assess the same subject throughout the study.

The schedule of these safety assessments is provided in the SOE ([Table 2](#)), and the study-specific procedures for completion of these assessments are detailed below.

Assessments should not be performed on subjects who have missed two or more consecutive study drug doses immediately before the Week 1, Week 2, Week 3, or Week 4 / Premature Discontinuation visits.

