9.3.4.1. Primary Efficacy Endpoint Analysis

The MADRS is a 10-item scale whose total score can range from 0 to 60. The primary efficacy variable is change from Baseline in MADRS total score at Week 4, for testing superiority of SP-624 vs. placebo in adults with major depressive disorder. The analysis will be completed using observed data without imputation. Scores will be taken at 4 weeks regardless of subject discontinuation from treatment. Subjects will not be treated with any other antidepressant medication until at least the completion of the Week 5 visit.

The change from Baseline in MADRS total score at Week 4 will be analyzed from the difference in least square mean change using MMRM, with change from Baseline in MADRS total score at each visit as the response variable. The MMRM model will include age, weight, and baseline

MADRS total score as covariates, with factors for treatment, visit (Weeks 1, 2, 3, and 4; as a categorical variable), treatment by visit interaction term, gender, and site as a fixed effect. An unstructured covariance matrix will be used for the within-subject correlation. Kenward-Rogers approximation will be used to calculate the denominator degrees of freedom. The primary efficacy endpoint will be calculated using an estimate statement. Subjects from low enrolling sites may be pooled in order to help with model convergence.

In the event of a model which fails to converge, additional strategies to address convergence may be required such as alternative covariance structures, using a maximum likelihood versus restricted maximum likelihood (REML) estimation, or dropping variables.

The protocol may include approximately 40 sites and sites with less than 10 subjects will be pooled to obtain at least 10 subjects. Sites would be pooled in order of the site number and, if necessary, the last un-pooled site will be pooled with the last set of sites pooled.

Additional variables of interest that may be evaluated as covariates will be identified in the SAP, such as age of onset of depression and number of lifetime episodes.

Additionally, results from the primary outcome will be summarized for the PP population.

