#### **8.1.1** Efficacy Assessment Windowing

For all efficacy analyses, windowing will be applied to ensure study day of assessment does not fall too far from scheduled assessment day. Assessments will be considered part of the scheduled visit window if they fall within  $\pm$ 3 days of the nominal study visit day. In the event of multiple assessments within the same visit window, the assessment closest to the nominal study day will be used. In the event of a tie, the

Form STAT401.V3 Page 9 of 23

Client/Project	Arrivo/Sirtsei 201
Version and Date	V01 August 26, 2022

earliest study day will be used. A visit must be completed within 2 days of last treatment dose to be included as a treatment period visit. Visits completed 3 or more days after last dose will be excluded from the treatment period analysis. Follow-up period windowing will be relative to date of last dose of study drug: assessments completed 3 to 10 days after the last dose of study drug will be windowed to the Week 5/1-Week Follow-up Visit.

Efficacy assessment listings will include both the reported and windowed visit labels. Any assessment completed outside of the windows for which that particular assessment was scheduled to be completed per the protocol will be labeled as "Out of Window".

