**Table 8.1, Handling of Intercurrent Events** 

Estimand	Intercurrent Event	Rule / Rationale
Primary	Premature discontinuation /	Hypothetical "as own treatment" strategy. Clinical
	Permanent treatment	course is the same as other subjects in the same
	discontinuation	treatment group, who had not discontinued study
		treatment.
		Exclude observations that occur more than 3 days
		after the last dose of study drug for subjects who
		discontinue. The objective of the study is to
		evaluate the effect of SP-624 subjects who are
		provided drug to take on a standard schedule up to 4
		weeks. After 3 days, the drug should be cleared
		from all subjects, so the inclusion of any such data
		point is inconsistent with the goal of the estimand.
	Drug non-compliance / Missed	Treatment policy strategy.
	study medication	Some degree of non-compliance missed doses
		would be expected to occur in standard use.
	Protocol deviations not leading	Treatment policy strategy
	to study discontinuation	Overall, if not sufficient to lead to subject removal,
		the expectation is that they would not significantly
		impact subject results.
	Concomitant medications in	Treatment policy strategy
	violation of the protocol	This is expected to be a rare event in this clinical
		trial and treatment effect will be estimated
		irrespective of concomitant medication violations.

The hypothetical "as own treatment" strategy was selected for premature discontinuation or treatment discontinuation intercurrent events to evaluate the effect of treatment with respect to its pharmacologic efficacy. For the change from week 4 to week 5 follow-up secondary analysis, only subjects that were included in the week 4 primary analysis will be used. This should provide the most unbiased data for this

Form STAT401.V3 Page 12 of 23

Client/Project	Arrivo/Sirtsei 201
Version and Date	V01 August 26, 2022

phase 2 study to inform future studies. The treatment policy strategy will be used for all other defined intercurrent events.

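### Protocol 7.2.4 tells sites not to rate subjects after two missed doses, which contradicts protocol 9.3.4.1 and leaves the SAP's treatment-policy rule for missed doses only partly workable

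*Protocol*

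**What the plan says.** **Protocol 7.2.4**, on efficacy ratings: "Assessments should not be performed on subjects who have missed two or more consecutive study drug doses immediately before the Week 1". The sentence then names the next two weekly visits and the Week 4 / Premature Discontinuation visit as well.

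**Protocol 9.3.4.1**, on the primary endpoint: "Scores will be taken at 4 weeks regardless of subject discontinuation from treatment".

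**Protocol 5.4**, on early stopping: as a minimum, "every attempt should be made to complete the Week 4 / Premature Discontinuation procedures". Table 2 schedules the MADRS in that column. For longer follow-up, 5.4 names safety only: such subjects "should continue to be followed for scheduled safety assessments according to the SOE".

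**SAP Table 8.1** assigns treatment policy to missed study medication. The rationale, which begins "Some degree of non-compliance missed doses", is that this is to be expected in ordinary use. Stopping treatment is handled differently: the text under the table says that a hypothetical "strategy was selected for premature discontinuation or treatment discontinuation intercurrent events".

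**SAP 8.1.1** sets the timing rule: "A visit must be completed within 2 days of last treatment dose" to count in the treatment period. Visits three or more days after the last dose leave the treatment-period analysis, and assessments 3 to 10 days after it are assigned to the Week 5 follow-up. For discontinuers, Table 8.1 puts the cut-off at more than three days.

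Neither Table 8.1 nor SAP 2.2, which lists changes to the planned analyses, mentions the instruction in 7.2.4.

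**The concern.** The protocol gives sites incompatible instructions on the primary outcome. Because 7.2.4 is worded as a recommendation, the roughly 40 sites may resolve the conflict in different ways, and a reader could not tell which instruction was followed.

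Where the rating is withheld, the score is missing because of adherence after randomisation. Adherence may differ between arms through tolerability or lack of effect. SAP 8.3.5.5 accepts that the MMRM relies on data being missing at random, and the withheld ratings are data that would help to judge that assumption. They also include scores that a treatment-policy strategy for missed doses is meant to use. No analysis rule can recover a rating that was not taken.

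**Working it through.** **1. The plan's own figure.** Inputs from protocol 9.1 and 9.3.1: difference 3, SD 9.2, two-sided alpha 0.05, power 80%.

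n per arm = 2(z₀.₉₇₅ + z₀.₈₀)²σ²/Δ² = 2 × (1.960 + 0.842)² × 9.2² / 3² = 147.7, so 148 (149 by the t-test version). Power at 150 per arm = Φ(3/(9.2 × √(2/150)) − 1.960) = Φ(2.824 − 1.960) = 0.806. The stated 150 per arm is reproduced and is not in dispute.

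**2. Protocol against protocol.** Take a subject who stopped dosing at least two doses ago and attends the Week 4 / Premature Discontinuation visit. Under 7.2.4 the MADRS is not done. Under 5.4 and Table 2 it is one of the procedures to attempt. Under 9.3.4.1 a Week 4 score is taken despite the stop. The instructions cannot all be met.

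**3. Protocol against SAP.** Dosing is once daily, so the SAP clock is visit day minus last dose day.

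| Case | Days since last dose | Protocol 7.2.4 | SAP | Conflict |
|---|---|---|---|---|
| Days 12 and 13 missed, visit Day 14, dosing resumed to Day 28 | Visit precedes last dose | Not rated | Week 2 score kept, treatment policy | Yes |
| Last dose Day 26, Days 27 and 28 missed, visit Day 28 | 28 − 26 = 2 | Not rated if the visit-day dose counts | Kept by 8.1.1 | Yes, on that reading |
| Days 26 and 27 missed, dose taken on Day 28 | 0 | Not rated if the gap still counts as directly before the visit | Kept by 8.1.1 | Yes, on that reading |
| Last dose Day 25, no dose on Days 26 to 28, visit Day 28 | 28 − 25 = 3 | Not rated | Dropped by 8.1.1; for a discontinuer, Table 8.1's cut-off would keep it | None under 8.1.1 |
| Permanent stop, last dose Day 10, visit Day 14 | 14 − 10 = 4 | Not rated | Not in the treatment period; assigned to Week 5 by 8.1.1 | None for the primary analysis; a score for change to Week 5 may be lost |

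The second row depends on counting the visit-day dose. Protocol 3.2.3 supports this: the Week 4 PK sample is due about 2 to 10 hours after dosing, so a dose is expected that day. The fourth row shows that the two SAP cut-offs disagree at exactly three days.

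**4. Size, as illustration only.** The documents give no rate for runs of two or more missed doses. Assume that a fraction f of Week 4 scores is lost outright, with nothing recovered through the MMRM:

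| f (assumed) | Scores lost per arm (150f) | Scores left per arm | Power | Overstatement, 3f points |
|---|---|---|---|---|
| 0 | 0 | 150 | 0.806 | 0 |
| 5% | 7.5 | 142.5 | 0.786 | 0.15 |
| 10% | 15 | 135 | 0.764 | 0.30 |
| 15% | 22.5 | 127.5 | 0.740 | 0.45 |

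The last column further assumes that the affected SP-624 subjects change by the placebo 9 points instead of 12. The difference with them included is then 3 − 3f. Leaving them out gives 3, so the overstatement is f × (12 − 9).

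**The case against.** The best defence is that protocol Section 9 calls its analyses proposed and leaves the detail to the SAP. The SAP treats discontinuation hypothetically and discards treatment-period scores from three days after the last dose. For permanent discontinuers, 7.2.4 therefore largely agrees with the final primary analysis. That stands. It does not reconcile 7.2.4 with 9.3.4.1, and SAP 2.2 records no departure from 9.3.4.1.

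Second, SAP 8.3.5.1 frames efficacy as if subjects had dosed as directed for four weeks, so an effect under adherence could be the intended target. This is a fair reading of that sentence, but the missed-dose row of Table 8.1 names treatment policy explicitly. The SAP is in tension with itself here, and 7.2.4 settles part of the matter without saying so.

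Third, 7.2.4 can be read as a specific exception to 5.4, whose continued follow-up is for safety. This makes 5.4 weaker support than 9.3.4.1.

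A reader might also infer more than the documents support:

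- *That the Week 4 scores the SAP needs are never collected.* The instruction covers only gaps of two or more doses directly before a visit. Subjects with one missed dose, or an earlier gap followed by resumed dosing, are still rated.
- *That subjects generally drop out of the mITT population.* Only those with no other post-dose efficacy rating would, and the Week 5 MADRS and CGI-S are outside the instruction.
- *That the loss comes on top of the 20–30% dropout.* Many affected subjects would be discontinuers already counted there.
- *That the effect is overstated by up to 0.45 points.* This takes an assumed rate, assumes that benefit is lost entirely after as few as two missed doses, ignores earlier ratings used by the MMRM, and counts scores that 8.1.1 would drop anyway.

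**Conclusion.** The point holds in two parts of different strength. Within the protocol, 7.2.4 directly contradicts 9.3.4.1 and sits badly with 5.4 for subjects who have stopped dosing. Against the SAP the mismatch is partial: treatment policy for missed doses cannot be carried out for temporary gaps directly before Weeks 1 to 3, nor for a few Week 4 patterns that turn on how the visit-day dose is counted. The SAP primary analysis does not depend on scores after permanent discontinuation.

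The number of subjects affected is unknown. The 5–15% range is an assumption, and the resulting power and bias figures lean towards the upper end, because at Week 4 the true SAP conflict is confined to narrow cases. The contradiction itself rests on the text alone and needs none of these figures.

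**What to change.** Replace the sentence in 7.2.4 so that all efficacy scales are completed at every attended visit, including Premature Discontinuation, whatever the number of missed doses, and the dates of the last dose and of missed doses are recorded. The SAP then decides use:

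- Scores after temporary gaps enter the primary analysis under treatment policy.
- Scores after permanent discontinuation are flagged and kept for a supportive analysis regardless of discontinuation, in line with 9.3.4.1.
- The cut-offs in 8.1.1 (three or more days) and Table 8.1 (more than three days) are made the same. Changing 7.2.4 alone would not be enough, because 8.1.1 would still govern which Week 4 scores count.

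The SAP is dated August 2022 and the protocol estimated the last visit for November 2021, so rating may already be complete. In that case, report the number of withheld ratings by arm and visit, and state in the SAP that the missed-dose strategy is treatment policy only for gaps shorter than two doses before a visit.

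The cost is a short protocol amendment and a note to sites, or an SAP clarification and one table. No visits or procedures are added, since the scales are already scheduled. The downside is that the estimate will include some non-adherent scores and may be slightly smaller.
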